However, by the time we made the decision to change our inclusion criteria, enrollment exceeded 5,000 patients. We plan to include all eligible patients enrolled through 1/2/23 in analyses, because we have already pulled enrollment data on these patients.

Power Analysis

Data will be collected from 5,000 patients who were discharged to SNFs. We expect to have 80% power to detect a 4% increase (34% to 38%) in selection of P-SNFs at two-tailed p < .05.

Analysis Approach

Analyses described below represent our planned analyses assuming statistical assumptions are met. If assumptions are not met, we will run alternative tests appropriate for the outcome distribution (e.g., non-parametric tests).

Recent work suggests that OLS regressions are appropriate in randomized experiments with binary outcome variables such as ours (Gomilla, 2021). Therefore, for binary outcome variables, we default to running OLS regressions.

Some of our originally preregistered outcome descriptions mentioned comparing Time 1, before the Repisodic app was deployed, to Time 2, during the study, after launch of the app. Upon learning that it is infeasible to obtain comparable Time 1 measurements and include them in analysis, we decided to omit Time 1 to focus analyses entirely on comparing outcomes during the study period (i.e., the primary causal investigation).

Primary Outcomes

P1: Overall LoS (system/case manager level) [Time Frame: 24 months or as long as it takes to reach N=5,000, whichever occurs first]

Difference in LoS (in days) for patients as a function of case manager study condition

Analysis: We will run a gamma regression to test whether LoS differs between patients with a case manager in Default List versus P-SNF Top-Sorted groups.

P2: P-SNF placement (system/case manager level) [Time Frame: 24 months or as long as it takes to reach N=5,000, whichever occurs first]

Difference in proportion of discharges of patients to P-SNFs (out of P-SNFs + NP-SNFs) as a function of case manager study condition.

Analysis: We will run a beta regression to test whether there is a difference in the proportion of patient discharges to P-SNFs for the case manager Default List and P-SNF Top-Sorted groups.

P3: P-SNF pre-selection (case manager level) [Time Frame: 24 months or as long as it takes to reach N=5,000, whichever occurs first]

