Number of P-SNFs selected by case managers for inclusion in the patients' lists, to assess the direct impact of Repisodic changes on case manager behavior; this is the first decision in the process, before patients' selections and SNF availability factor into the final discharge decision and placement.

Analysis: We will run a negative binomial regression to test whether the number of P-SNFs preselected differs as a function of case manager study arm, clustering standard errors at the case manager level. P4: P-SNF selection (case manager level) [Time Frame: 24 months or as long as it takes to reach N=5,000, whichever occurs first]

Number of P-SNFs selected by patients to help assess the downstream impact of Repisodic changes on patient behavior following case manager pre-selection, again omitting the influence of SNF availability.

Analysis: We will run a negative binomial regression to test whether the number of P-SNFs selected differs as a function of case manager condition, clustering standard errors at the case manager level.

Note: Retrospective data prior to the study period suggested that only ~15% of patients indicate their selections in the Repisodic app. Therefore, data will be missing for many patients in this analysis. However, we will run this analysis on patients with available data.

P5: P-SNF percent selected (case manager level) [Time Frame: 24 months or as long as it takes to reach N=5,000, whichever occurs first]

Percentage of patients who selected at least one P-SNF, to help assess the downstream impact of Repisodic changes on patient behavior following case manager pre-selection.

Analysis: We will run a beta regression to test whether the percentage of patients who selected one or more P-SNFs differs as a function of case manager condition, clustering standard errors at the case manager level.

Note: Retrospective data prior to the study period suggested that only ~15% of patients indicate their selections in the Repisodic app. Therefore, data will be missing for many patients in this analysis. However, we will run this analysis on patients with available data.

P6: LoS (patient/caretaker level) [Time Frame: 24 months or as long as it takes to reach N=4,000, whichever occurs first]

LoS for patients (in days).

Analysis: We will run a gamma regression to test whether LoS differs as a function of patient condition, clustering standard errors at the case manager level.

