P7: P-SNF placement (patient/caretaker level) [Time Frame: 24 months or as long as it takes to reach N=5,000, whichever occurs first]

Patient was discharged to a P-SNF: yes/no.

Analysis: We will run an OLS regression to test whether patient P-SNF placement rates differ as a function of patient condition, clustering standard errors at the case manager level.

P8: P-SNF selection (patient/caretaker level) [Time Frame: 24 months or as long as it takes to reach N=5,000, whichever occurs first]

Patient selected a P-SNF for discharge: yes/no. This is a more direct reflection of patient behavior, not yet moderated by bed availability and other real-world considerations that affect Outcome 7.

Analysis: We will run an OLS regression to test whether patient P-SNF selection rates differ as a function of patient condition, clustering standard errors at the case manager level.

Note: Retrospective data prior to the study period suggested that only ~15% of patients indicate their selections in the Repisodic app. Therefore, data will be missing for many patients in this analysis. However, we will run this analysis on patients with available data.

Secondary Outcomes

S1: Time to pre-select a SNF (case manager level) [Time Frame: 24 months or as long as it takes to reach N=5,000, whichever occurs first]

Time to pre-select a SNF/SNF list in Repisodic (in minutes), from the time that the case manager first signs into the iPad to when the case manager saves the list to send to the patient. This measure excludes cases in which the task was not completed.

Analysis: We will run an OLS regression to test whether the time to pre-select a SNF list in Repisodic differs as a function of case manager condition, clustering standard errors at the case manager level.

S2: Time to select a SNF (patient/caretaker level) [Time Frame: 24 months or as long as it takes to reach N=5,000, whichever occurs first]

Time to select a SNF in Repisodic (in minutes), from the time that the patient first signs or is signed into the iPad to when the patient clicks to send the list to the case manager. This measure excludes cases in which the task was not completed.

Analysis: We will run an OLS regression to test whether the time to select a SNF list in Repisodic differs as a function of patient condition, clustering standard errors at the case manager level.

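### P5 (primary): beta regression cannot take 0% or 100%, yet the SAP fixes neither the analysis row nor a rule for such values, which its own figures make unavoidable

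*SAP*

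**What the plan says.** P5 is one of eight primary outcomes and is headed as a case manager level outcome. It is defined as "Percentage of patients who selected at least one P-SNF". The analysis is a "beta regression to test whether the percentage of patients who selected one or more P-SNFs differs as a function of case manager condition", with standard errors clustered by case manager. The note to P5 warns that "only ~15% of patients indicate their selections in the Repisodic app" and restricts the analysis to patients with data.

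Three other places bear on it:

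- Analysis Approach states that "for binary outcome variables, we default to running OLS regressions".
- The same section says that, if assumptions fail, "we will run alternative tests appropriate for the outcome distribution (e.g., non-parametric tests" is the course to be taken.
- P8, on essentially the same event, uses an "OLS regression to test whether patient P-SNF selection rates differ as a function of patient condition, clustering standard errors at the case manager level".

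The SAP gives no analysis row for P5, no treatment of percentages equal to 0 or 100, no weighting by number of patients and no minimum caseload.

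**The concern.** The beta distribution lives strictly between 0 and 1, and each natural reading of P5 meets its boundary.

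- **One row per case manager.** The heading and the word percentage point this way. The clustering phrase is then redundant, and managers with only a few recorders will often be at exactly 0% or 100%.
- **One row per patient.** The clustering phrase points this way, and P3, P4 and S1 carry the same heading label with list- or patient-level outcomes. Every value is then 0 or 1, and no beta regression can be fitted.

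The analyst must therefore add a step that the SAP does not contain. Dropping boundary managers, squeezing them inside the interval and fitting a zero/one-inflated model are different analyses. At stake are the size of a primary effect estimate and the protection that prespecification should give.

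**Working it through.** **The SAP's own figure.** The Power Analysis section claims "80% power to detect a 4% increase (34% to 38%) in selection of P-SNFs" with 5,000 patients. A normal approximation with 5,000 patients split 70:104 and no clustering gives 82.3% (81.5% with continuity correction). With 5,000/174 = 28.7 patients per manager and an assumed ICC of 0.002, the design effect is 1 + 27.7 × 0.002 = 1.055 and power is 80.3%. The figure is reproducible, but it describes all 5,000 patients and not the subset with P5 data.

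**Inputs.** From the SAP: 5,000 patients; about 15% recording; 70 and 104 active case managers; 34% and 38%. Assumed: ICC 0 to 0.1; caseloads even, random (multinomial) or uneven (gamma, CV 1); in-study recording equal to the pre-study rate; 34%/38% as P5's rates.

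**Step 1: the likelihood.** Up to a constant, the log-density is (μφ − 1)·log y + ((1 − μ)φ − 1)·log(1 − y). With μ = 0.36 and φ = 5 the coefficients are 0.8 and 2.2, so it is −∞ at y = 0 and at y = 1. With μ = 0.5 and φ = 1 both coefficients are −0.5 and it is +∞. Such rows cannot be used.

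**Step 2: recorders per manager.** 0.15 × 5,000 = 750; 750/(70 + 104) = 4.3.

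**Step 3: boundary managers, by hand.** With n recorders and no ICC, the chance of 0% or 100% is p^n + (1 − p)^n.

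- n = 4: 0.0134 + 0.1897 = 20.3% at p = 0.34; 0.0209 + 0.1478 = 16.9% at p = 0.38.
- n = 5: 13.0% and 10.0%.
- Even caseloads (120 managers with 4, 54 with 5): 18.0% in the default arm and 14.7% in the top-sorted arm, so (70 × 18.0% + 104 × 14.7%)/174 = 16%.

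Simulation over the ICC range gives 16–24% (even), 25–31% (random) and 35–39% (CV 1).

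**Step 4: what dropping does, by hand.** For n = 4, the mean among managers not at a boundary is (p − p⁴)/(1 − p⁴ − (1 − p)⁴):

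- p = 0.34: 0.3266/0.7969 = 41.0%.
- p = 0.38: 0.3591/0.8314 = 43.2%.

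The 4.0-point difference becomes 2.2 points, because more managers are lost at 0% than at 100%, and more of them in the lower-rate arm.

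**Step 5: simulation.** Beta-binomial data, 2,000 runs per cell, 750 recorders. Beta fits use one row per manager with data and a sandwich standard error. The squeeze is (y(M − 1) + 0.5)/M for M rows.

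| Method | Estimated difference (true 4.0 points) | Power | Rejection under the null (36% in both arms) |
|---|---|---|---|
| Drop boundary managers | 1.8–2.3 (even, random); 2.4–2.7 (CV 1) | 8–14% | 4.3–5.8% |
| Squeeze | 3.9–4.1 (even); 3.4–3.7 (random); 2.9–3.2 (CV 1) | 10–17% | 4.8–7.1% |
| Zero/one-inflated, overall mean | 3.8–4.1 | not computed | not computed |
| Patient-level OLS, clustered | 3.9–4.2 | 14–21% | 4.7–6.3% |

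Dropping also lifts the apparent control rate from 34% to 39–42%. Drop and squeeze differ by 3.7–4.4 points on average in absolute value within a trial, have opposite signs in 26–35% of trials and give different verdicts at .05 in 17–22%. Reporting whichever of the two is significant rejects a true null in 8.5–11.6%.

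**Step 6: sensitivity to the number of recorders.** The SAP says that "enrollment exceeded 5,000 patients" without giving the total; 900 is 15% of an assumed 6,000. Rows other than 750 use ICC 0 and 0.05 and 800 runs per cell.

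| Recorders | Managers at 0% or 100% | Difference after dropping |
|---|---|---|
| 500 | 34–46% | 0.9–2.3 |
| 750 | 16–39% | 1.8–2.7 |
| 900 | 10–33% | 2.4–2.8 |
| 1,250 | 4–26% | 2.9–3.2 |

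**The case against.** The best defence is that Analysis Approach already covers this: the planned models hold only if their assumptions are met, alternatives are promised otherwise, and binary outcomes default to OLS. That shows the fix is in keeping with the SAP. It does not settle P5. The fallback names no trigger, no replacement model and no rule for 0 or 1, and P5 is written as a percentage with its own named model, so the binary default does not apply as written. The failure is also foreseeable, so leaving it to a contingency clause defers the choice until the data are seen.

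Several points on size do stand:

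- The heavy shrinkage belongs to dropping. The zero/one-inflated estimate, and the squeeze with even caseloads, are close to unbiased. A milder adjustment, (x + 0.5)/(n + 1), gave 2.9–3.1 points with 15–20% power.
- The opposite-sign figure is largely noise from low power; a check under the null gave 42%. The bias from dropping is the firmer evidence.
- The 8.5–11.6% false-positive rate is a worst case. Each method used alone stays near 5%.
- Naming the row and a boundary rule, or a zero/one-inflated model, would also cure the defect.

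P2 uses beta regression too, without stating a row. At about 29 patients per manager boundary values are rare unless caseloads are very uneven; with CV 1 some 7–10% of managers reach them. Bias there is small, and this point is confined to P5.

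**Conclusion.** The concern holds. P5's stated primary model cannot be run on the expected data without a choice that the SAP does not make. That conclusion needs no assumption beyond at least one manager at 0% or 100%, which occurred in every simulated trial at 10%, 15% and 30% recording. On patient rows the model fails outright.

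The size is less certain. At 750 recorders, 16–39% of managers are at a boundary, and the estimate of a true 4.0-point difference runs from about 1.8 to 4.1 points depending on how they are handled. This rests on the assumed ICC, caseload spread, in-study recording near 15% and rates of 34% and 38%. More recording shrinks the problem: at 1,250 recorders the boundary share is 4–26%.

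**What to change.** Replace the P5 analysis sentence with one to this effect:

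> Among patients with selection data, with one row per patient, we will regress an indicator of having selected one or more P-SNFs (yes/no) on case manager condition by OLS, with cluster-robust standard errors by case manager.

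This fixes the row, gives the clustering phrase a purpose and needs no boundary rule. It follows the SAP's own default for binary outcomes and mirrors P8, with case manager condition in place of patient condition.

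The cost is one sentence and no new data. Project Status says outcomes have not been looked at by condition, so the change can be made blind. The estimate becomes patient-weighted instead of giving each randomized manager equal weight; this could matter if selection rates vary with caseload, which was not examined here. Power for 4 points stays at about 14–21% with 750 recorders, so the change repairs the estimate and the prespecification, not the information available.

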Post-acute Care Preferred Provider Network Skilled Nursing Facility Selection as a Function of Repisodic Mobile Application Settings

Statistical Analysis Plan

February 16, 2023

Statistical Analysis Plan

Brief Summary

This study tests whether changing the relative order of presentation of post acute care skilled nursing facilities (SNFs) in the Repisodic application, i.e., presenting preferred SNFs (P-SNFs) first, increases selection of, and discharges to, P-SNFs and decreases lengths of stay (LoS) for Geisinger patients discharged to SNFs. Along with the order of P-SNFs, the study also assesses whether a short video reviewing the benefits of care coordination in P-SNFs increases patient election to transfer to one.

Randomization

Case managers were randomized to one of two conditions upon their account creation (Default List vs. P-SNF Top-Sorted List). Patients were independently randomized to one of two conditions when Repisodic lists were generated for them (Full List/Full Map/Default Video vs. P-SNF List/P-SNF Map/P-SNF Video).

Project Status

All interventions were launched on 5/28/2021 and data collection is ongoing. Outcome data have not been examined as a function of experimental condition. However, only patients who are ultimately discharged to a SNF can be included in our analyses, and not all randomized patients are ultimately discharged to SNFs (e.g., patients who were discharged home, despite initially being considered for a SNF). So, to assess enrollment progress throughout the study, we need to extract data on patients' discharge locations and remove patients who were not discharged to a SNF.

Our original primary outcome time frame was 12 months or as long as it takes to reach N=4,000, whichever occurs first. However, we decided to extend our outcome time frame to 24 months or as long as it takes to reach N=5,000 patients. We made this change because we noticed an imbalance in the number of case managers assigned to the two conditions, such that by chance, there were more active case managers in the P-SNF top-sorted condition (N = 104 as of 1/2/23) compared with the default list condition (N = 70 as of 1/2/23). We ran a simulation power analysis to reassess how many patients should be in our final sample size, given the imbalance in case manager assignment, and determined that 5,000 patients would yield sufficient power to detect a 4% increase in P-SNF selection.

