Note: Retrospective data prior to the study period suggested that only ~15% of patients indicate their selections in the Repisodic app. Therefore, data will be missing for many patients in this analysis. However, we will run this analysis on patients with available data.

Other Outcome Measures

O1: LoS for patients who had a P-SNF as an option (patient/caretaker level) [Time Frame: 24 months or as long as it takes to reach N=5,000, whichever occurs first]

LoS for patients (in days). Excluding patients who did not have at least one P-SNF on the full list they were provided.

Analysis: We will run a gamma regression to test whether LoS differs as a function of patient condition, clustering standard errors at the case manager level.

O2: P-SNF placement for patients who had a P-SNF as an option (patient/caretaker level) [ Time Frame: 24 months or as long as it takes to reach N=5,000, whichever occurs first]

Patient was discharged to a P-SNF: yes/no. Excluding patients who did not have at least one P-SNF on the full list they were provided.

Analysis: We will run an an OLS regression to test whether patient P-SNF placement rates differ as a function of patient condition, clustering standard errors at the case manager level.

O3: P-SNF selection for patients who had a P-SNF as an option (patient/caretaker level) [Time Frame: 24 months or as long as it takes to reach N=5,000, whichever occurs first]

Patient selected a P-SNF for discharge: yes/no. Excluding patients who did not have at least one P-SNF on the full list they were provided. This is a more direct reflection of patient behavior, not yet moderated by bed availability and other real-world considerations that affect Outcome O2.

Analysis: We will run an an OLS regression to test whether patient P-SNF selection rates differ as a function of patient condition, clustering standard errors at the case manager level.

Note: Retrospective data prior to the study period suggested that only ~15% of patients indicate their selections in the Repisodic app. Therefore, data will be missing for many patients in this analysis. However, we will run this analysis on patients with available data.

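### The app-selection outcomes (P5, P8, O3, and also P4 and S2) are analysed only in patients who record a choice after randomisation, with no check on whether response differs by arm

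*SAP*

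**What the plan says.** The SAP's Randomization section states: "Patients were independently randomized to one of two conditions when Repisodic lists were generated for them". The patient conditions are "Full List/Full Map/Default Video vs. P-SNF List/P-SNF Map/P-SNF Video", so list, map and video all differ by patient arm. Case managers are randomised separately, to a default or a top-sorted list.

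The same note stands under P4, P5, P8, S2 and O3. It says that in retrospective pre-study data "only ~15% of patients indicate their selections in the Repisodic app", that "data will be missing for many patients in this analysis", and that "we will run this analysis on patients with available data". S2 adds: "This measure excludes cases in which the task was not completed".

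The SAP plans no comparison of response by arm for these outcomes. It gives no full-denominator version, weighting, imputation or bounds, and no limit on interpretation. Under P8 it presents selection as a more direct measure of patient behaviour than placement (P7).

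**The concern.** Recording a choice is a behaviour that follows randomisation and may be affected by it. For P8, S2 and O3 the route is direct, because recording follows the patient's arm-specific list, map and video. For P4 and P5 it is indirect: the randomised factor is the case manager's list order, which can reach the patient only through the list that the case manager builds.

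A comparison among recorders is protected by randomisation only if the arms do not differ in which patients record. The SAP treats the missing selections as lost numbers and plans nothing to examine that condition. Three of its eight primary outcomes (P4, P5, P8) rest on this subset. A difference in who used the app could be reported as a difference in what patients chose, or could hide one.

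**Working it through.** **Inputs from the SAP.** Target 34% vs 38% selecting a preferred facility, two-sided 0.05, 80% power, 5,000 patients (Power Analysis); pre-study recording about 15% (notes under the five outcomes); 104 and 70 active case managers (Project Status).

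**Assumptions.** 34% is taken as the choice rate among recorders, which the SAP does not say. Arms are 2,500 each. Clustering is ignored. In-trial response is not given, so 10% to 20% is used as a range.

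**The plan's own figure.** Power = Φ[(0.04 − 1.96·SE₀)/SE₁], with SE₀ pooled and SE₁ unpooled.
- 2,500 per arm: SE₀ = √(0.36 × 0.64 × 2/2,500) = 0.01358 and SE₁ = √((0.34 × 0.66 + 0.38 × 0.62)/2,500) = 0.01356, giving 83.8%.
- Patients split 70:104 (about 2,011 vs 2,989): 82.3%, or 81.5% with continuity correction.

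The stated 80% is therefore plausible for a clustered simulation in which every patient contributes. The 4-point target is a fair yardstick for P5, P8 and O3. It does not apply to a count (P4) or a time (S2).

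**Creating 4 points with no true effect.** Let r be response in the reference arm, x the extra response in the other arm, and q the share of extra responders who choose a preferred facility. The observed rate in the other arm is (0.34r + qx)/(r + x). Setting this to 0.38 gives x = 0.04r/(q − 0.38). With r = 15%:

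| q | x (points) | response in other arm |
|---|---|---|
| 100% | 0.006/0.62 = 1.0 | 16.0% |
| 75% | 0.006/0.37 = 1.6 | 16.6% |
| 60% | 0.006/0.22 = 2.7 | 17.7% |
| 50% | 0.006/0.12 = 5.0 | 20.0% |

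At q = 34% the bias is zero for any x. With q = 100%, x is 0.6 points at r = 10% and 1.3 points at r = 20%. For the first row, 1.0 point is about 24 patients in 2,500.

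**The same bias from lower response.** If only patients who would choose other facilities record less often, response falls to 0.051/0.38 = 13.4% and the observed rate is again 38%.

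**Hiding a true 38%.** If all extra responders choose non-preferred facilities, the observed rate falls to 34% when response rises by 0.15 × 0.38/0.34 − 0.15 = 1.8 points.

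**Would a test of response show it?** For 15% vs 16% at 2,500 per arm, SE = √(0.155 × 0.845 × 2/2,500) = 0.01024, so z = 0.98 and p = 0.33. Power to detect that difference is about 16%.

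**Would a full-denominator outcome show it?** With no record counted as no, the first row of the table gives 0.15 × 0.34 = 5.1% vs 5.1 + 1.0 = 6.1%, the same direction as the artefact. In the lower-response case both arms stay at 5.1% and the artefact is exposed.

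**What bounds would show.** Suppose response is 15% vs 16%, observed selection in the higher-response arm is 38%, and arm moves response in one direction only. The excess share of responders is 0.01/0.16 = 6.25%. Trimming it gives (0.38 − 0.0625)/0.9375 = 33.9% to 0.38/0.9375 = 40.5%. The lower limit falls just below the other arm's 34%, so the apparent effect would not survive.

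**The case against.** The strongest reply is that a one-point difference creates the full target effect only in the extreme case where every extra responder chooses a preferred facility. The other rows need 1.6 to 5.0 points, and response unrelated to choice does no harm. This stands, and it is why the size is given as a range.

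A reader might infer that such a small difference would produce a false significant result. The figures do not support that. With about 375 and 400 recorders at 34.0% and 38.1% (0.061/0.16), z = 1.19 and p = 0.23 before clustering. Reaching p < 0.05 would take roughly 1.7 extra points of response if all extra responders choose preferred facilities, 2.9 if 75% do, 5.0 if 60% do and 9.6 if 50% do. The concern is bias in the estimate, not certain false positives.

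Other replies hold in part:
- The SAP does disclose the missing data, but only as missing numbers.
- P2, P7 and O2 measure placement and carry no such note, so the evidence on use of preferred facilities does not rest on P8 alone. But the SAP itself separates placement from selection because of bed availability, so these outcomes cannot validate a selection result.
- A completion time exists only for completers, so the restriction in S2 is partly inherent. Its result still needs the conditional label.

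**Conclusion.** The concern holds as a risk of bias that the SAP leaves unexamined. P5, P8 and O3, and P4 and S2 without the 4-point figure, condition on a behaviour that follows randomisation. At 15% base response, 1.0 to 5.0 points of differential response could create the whole target effect, depending on whether 100% or 50% of the extra responders choose preferred facilities.

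This rests on response being related to choice, on 34% applying to recorders, and on a pre-study response rate. The SAP does not show that response differs by arm or that 85% of trial patients lack a selection, and it does not say why patients fail to record one. A reader should not conclude that these outcomes are biased, only that the plan could not tell. Nor would equal response rates prove that bias is absent.

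**What to change.** Project Status says outcomes had not been examined by condition, so these steps could still be pre-specified at the SAP's date.

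1. For both randomised factors, report and compare the proportion with a recorded selection by arm. State that a non-significant difference does not exclude bias.
2. Add to P5, P8 and O3 a version over all SNF-discharged patients in that outcome's set: recorded a selection including at least one preferred facility, yes or no, with no record counted as no. Read it as a composite of app use and choice. This set is itself limited to patients discharged to a SNF, so it restores the outcome's full analysis set and not everyone randomised.
3. Label the available-data results for P4, P5, P8, S2 and O3 as conditional on app response.
4. For P5, P8 and O3, add a simple tipping-point or bounds analysis showing how far the observed response difference could move the result. Claim a selection effect only if it survives. Agreement in direction between the planned analysis and step 2 is not an adequate rule, since both rise in the worked example.

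The cost is a few extra regressions and a short sensitivity table on data already held. The composite has a low event rate (about 5% under the assumptions above) and mixes app use with choice, so it accompanies the planned analysis and does not replace it.
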